### 5.2.2 Graphical presentation of results

Individual concentration-time profiles and mean profiles with SD bars will be presented for Days 1 and 7 (cohort 1) and Days 1 and 14 (cohort 2) and Period 1 and 2 (cohort 3).

Corporate Confidential Information

## 6 Statistical methods

Corporate Confidential Information

### 6.1 Primary objective

The primary variable is occurrence of an adverse event for cohort 1 and cohort 2 and evaluate response as reflected in percent of predicted FEV1 for cohort 3 of multiple doses of inhaled QBW276 in CF patients.

### 6.1.1 Variables

### 6.1.2 Descriptive analyses

Summary statistics of absolute and change from baseline values of percent of predicted FEV1 and all other spirometry parameters will be presented by treatment group and time.

Baseline is defined as the following:

- Cohorts 1 and 2: Result on day 1
- Cohort 3: Last Result before treatment in each period

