Corporate Confidential Information

0m sample is taken pre-dose; all post-dose samples (15 minutes – 6 hours) are timed from the start of inhalation

⁷ Central lab collection: Sodium, potassium, bicarbonate, creatinine, BUN, uric acid, chloride, albumin, calcium, alkaline phosphatase, total bilirubin, LDH, GGT, AST, ALT, PT/INR, amylase, lipase, CK, glucose, total cholesterol, and triglycerides

⁸ Local lab collection: sodium, potassium, chloride, bicarbonate

⁹ Only to be performed if subject's FEV1 is >80% of predicted at Screening

¹⁰ Serum pregnancy test

¹¹ Urine pregnancy test/dipstick

¹² Screening phase completion

Cohort 1 - Details for highly repetitive assessments

EPOCH	Visit Name	Visit Number	Day	Time (post-dose)	Vital Signs
SCREENING	Screening	1	-28 to -7	-	X
	Baseline	2	-1 -2 +0	-	X
TREATMENT	Day 1	101	1	0m ¹	X
				15m	
				30m	
				1h	X
				2h	
				4h	
				6h	X
	Day 2	102	2 -0 +1	0m ¹	X
	Day 7	103	7 -2 +2	0m ¹	X
				15m	
				30m	
				1h	X
				2h	
				4h	
	ET / EOS ²	199	11 -2 +2	-	X

¹ 0 minute (0m) sample is taken pre-dose; all post-dose samples (15 minutes – 6 hours

² Early termination/Study completion (study/treatment discontinuation and premature subject withdrawal should complete all these assessments)

Corporate Confidential
Information

PK blood collection	Local Lab Blood Chemistry
X	X
X	
X	X
X	X
X	X
X	X
X	X
X	X
X	
X	X
X	
X	X
X	X
X	X
X	X
X	X
X	

nhalation of the morning dose

Cohort 2 - 14 Days

EPOCH	SCREENING		TREATMENT					
	Visit Name	Screening	Baseline	Day 1	Day 2	Day 7	Day 14	ET/EOS ²
Visit Numbers ¹	1	2	101	102	103	104	199	
Study Day(s)	-28 to -7	-1 -2 +0		1	2 -0 +1	7 -2 +2	14 -2 +2	18 -2 +2
Informed consent	X							
Inclusion / Exclusion criteria	X	X						
Metabolite Screening Assay	X							
Corporate Confidential Information	X							
Randomization				X ³				
Study Drug Administration in Clinic in the Morning				X	X	X	X	
Medical history/current medical conditions	X	X						
Concomitant therapies	X	X	X	X	X	X	X	
Demography	X							
Vital Signs				See table below				
Body height	X							
Body weight	X	X			X ⁴	X ⁴	X	
Physical examination	X	X			X ⁴	X ⁴	X	
Spirometry	X	X	X ⁴	X ⁴	X ⁴	X ⁴	X	
Lung Volumes	X ⁶	X			X ⁴	X ⁴	X	
Multiple Breath Nitrogen Washout (MBNW)	X ⁶	X			X ⁴	X ⁴	X	
ECG evaluation	X	X	X ⁴		X ⁴	X ⁴	X	
Corporate Confidential Information		X			X	X	X	
PK blood collection ⁷				See table below				
Central Lab Blood Chemistry ⁸	X	X	X ⁴	X ⁴	X ⁴	X ⁴	X	
Central Lab Hematology	X	X	X ⁴		X ⁴	X ⁴	X	

EPOCH	SCREENING		TREATMENT				

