8.4.2 Vital signs

- Body temperature
- Blood pressure (BP)
- Pulse
- Respiratory rate
- Pulse oximetry

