### **1.3.2 Secondary objectives**

#### **Secondary Objective: Cohort 1 and 2**

- To evaluate the response to multiple doses of inhaled QBW276 on change in lung function (percent of predicted FEV1 and LCI) in patients with CF

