### **Cohort 1 and 2**

Cohorts 1 and 2 will consist of a 21 day screening period followed by a baseline visit and a 7 or 14 day Treatment Period in cohort 1 and 2, respectively. Adequate windows will be provided for patient's convenience. QBW276 will be administered on top of the patient's usual standard of care medications.

Study inclusion/exclusion criteria as well as medication use will be assessed at screening. Patients who meet the inclusion/exclusion criteria at screening will report to the study site on Day -1 at a time specified by the investigator, for the baseline assessments. All baseline safety evaluation results must be available prior to dosing on Day 1, hence, Day -1 assessments can be carried out up to 72 hours prior to Day 1 dosing.

Patients who meet all of the inclusion and none of the exclusion criteria at baseline will then report to the study site on Day 1 and will remain in the clinic until at least 6 hours after the first dose in the morning.

On Day 1, pre-dose safety, biomarker, PK blood draw, and urine collection will be performed. Following the pre-dose procedures, subjects will be randomized. Post-dose evaluations will include routine safety evaluations and blood for PK assessments. The patients will be asked to return to the study site for follow-up visits as specified on the respective assessment schedules.

[figure not shown]
Safety will be monitored by assessment of vital signs, physical examination, ECG, clinical laboratory evaluations (hematology, blood chemistry, and urinalysis), urine electrolytes, aldosterone in plasma, lung function, and monitoring of adverse events (AEs) throughout the study. PK (drug and metabolites) Corporate Confidential Information

measured in cohorts 1 and 2 will be compared with data from the healthy volunteer study.

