### **6.2.2 Descriptive analyses**

Absolute and change from baseline for all spirometry and LCI parameters will be listed by cohort, treatment, patient and visit/time and summarized by treatment group and dose level.

Summary statistics of these endpoints will be performed, split by the stratification of LCI results based on baseline FEV1 > 80% of predicted.

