### **6.2.5 Lung volumes and small airway measurements**

Lung Volume parameters include:

- FRC, RV/TLC, difference between SVC and FVC

Small airway measurements parameters include:

- FEV3, 1-FEV3, FEV6, FEV3/FVC, 1-FEV3/FVC, FEV3/FEV6, 1-FEV3/FEV6, FEV1/FEV6 (assessed by spirometry)

Parameters obtained from spirometry and Pulse oximetry at each time-point and changes from baseline will be summarized by treatment group. In cohort 3 summary stats will be provided by time within period.

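### Does the SAP's Day 1 baseline rule for Cohorts 1 and 2 leave change from baseline in LCI without a baseline?

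*SAP*

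**What the plan says.** SAP 6.1.2 opens with summaries of absolute values and changes from baseline for percent predicted FEV1 and the other spirometry parameters. It then defines baseline in two lines: "Cohorts 1 and 2: Result on day 1" and "Cohort 3: Last Result before treatment in each period". No other analysis baseline for Cohorts 1 and 2 is visible in the SAP.

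Other parts of the SAP need a baseline for more than spirometry:

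- SAP 1.3.2 gives the Cohort 1 and 2 secondary objective as "To evaluate the response to multiple doses of inhaled QBW276 on change in lung function", and names LCI beside FEV1.
- SAP 6.2.2 states: "Absolute and change from baseline for all spirometry and LCI parameters will be listed by cohort, treatment, patient and visit/time". SAP 6.2.3.1 adds plots of change, and correlations of change between spirometry and LCI.
- SAP 6.2.5 states: "Parameters obtained from spirometry and Pulse oximetry at each time-point and changes from baseline will be summarized by treatment group".

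On timing, SAP 1.4 has eligible patients "report to the study site on Day -1 at a time specified by the investigator, for the baseline assessments", and protocol 3.1 says the same. In protocol Table 8-1 the Baseline visit (Day -1, window -2/+0) and Day 1 are separate visits.

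**The concern.** The rule names a day, not a position relative to dosing, and the schedule does not place every assessment on that day. Two problems seem to follow.

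First, LCI is a named secondary endpoint whose objective is a change. If its baseline must be a Day 1 result and none is scheduled, the change at Day 7, Day 14 and end of study cannot be computed as written. If the rule is instead meant for spirometry alone, LCI has no visible definition.

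Second, nothing restricts the Day 1 result to one taken before dosing. Protocol 8.4.2 lists pulse oximetry as a vital sign, and vital signs are recorded several times on Day 1, some of them after the dose. A post-dose value used as baseline would absorb any early drug effect.

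At stake would be the definition of a secondary endpoint, and with it an analyst's freedom to choose the baseline after seeing data from very few placebo patients.

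**Working it through.** The plan gives no figure to reproduce; the check applies the rule to the schedule. Inputs are the Cohort 1 and Cohort 2 grids of protocol v04 Table 8-1 and their tables of repeated assessments. The pre-first-dose pattern is the same in both cohorts.

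| Assessment | Screening | Baseline (Day -1) | Day 1 | Results picked by a Day 1 rule |
|---|---|---|---|---|
| Spirometry | yes | yes | once, pre-dose | 1 |
| MBNW (LCI) | only if FEV1 > 80% | yes | none | 0 |
| Lung volumes | only if FEV1 > 80% | yes | none | 0 |
| Vital signs | yes | yes | 0 min, 1 h, 6 h | 3 (1 pre-dose, 2 post-dose) |

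The pre-dose footnote to Day 1 spirometry is legible for Cohort 1. The matching Cohort 2 footnote text is not shown, so pre-dose is inferred there.

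**Spirometry.** The rule picks exactly one scheduled value, the right one.

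**LCI.** A patient with screening FEV1 above 80% has 1 + 1 = 2 scheduled LCI results before the first dose, and any other patient has 0 + 1 = 1. The rule picks 0 in either case. The last scheduled result before dosing is the Baseline visit in both cohorts. For patients at or below 80% it is the only candidate. For those above 80%, the alternative is a Screening value from Day -28 to Day -7, at a visit not called Baseline.

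**Pulse oximetry.** If it follows the vital-signs timetable, three Day 1 results exist and one, at 0 min, precedes dosing. The link is loose: the vital signs listed in SAP 7.1 are blood pressure, pulse rate and temperature, and SAP 6.2.5 groups oximetry with spirometry. No analyst would take a 6-hour post-dose reading as a baseline.

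**Applying the Cohort 3 form of words.** Taking the last result before treatment gives Day 1 pre-dose for spirometry and oximetry, and the Baseline visit for LCI and lung volumes. These are the values an analyst would use anyway.

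**Patients affected.** Planned numbers are 8 + 8 = 16, of whom 6 + 6 = 12 are active and 2 + 2 = 4 placebo. If Cohort 2 is skipped, they are 8, 6 and 2. The number with screening FEV1 above 80% is not given.

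**What cannot be checked.** SAP 1.2 says the SAP was developed from protocol v02. MBNW plans differ between the SAP and v04: SAP 1.3.2 and 1.4 include LCI in Cohort 3, while protocol v04 section 8.3.1 confines it to Cohorts 1 and 2. Whether v02 scheduled MBNW on Day 1 is unknown. In the SAP, text is redacted after the section 6 heading, 6.1.1 is blank, 6.2.1 starts mid-sentence, and 6.2.4 appears only in the table of contents. An LCI baseline could have been stated in any of these places.

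**The case for a change.** The strongest case for a change is that the choice of LCI baseline is not quite empty. Patients in the LCI endpoint are those with screening FEV1 above 80%, who are the ones with two pre-dose LCI results. Inclusion criterion 7 requires their screening LCI to be at least 8, so a Screening baseline would be selected for being high and would tend to fall on repeat measurement without any drug effect. With 2 placebo patients per cohort, there is little to show how much of a fall is due to that. Protocol 3.3 also says that lung function in Cohorts 1 and 2 will support the Cohort 3 dose. One line in the SAP, modelled on its own Cohort 3 wording, would settle the matter.

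Some of this stands. On the visible text the definition does not extend to LCI, and a pre-dose qualifier would be tidier. But selection on the screening value is itself a reason to use the later visit, and that visit is already labelled Baseline in the schedule. The documents do not say that the SAP's change-from-baseline tables feed the review of the Cohort 3 dose.

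A rewrite would also need care. Cohort 1 patients may re-enter in Cohort 2, so the first dose would have to be the first dose in that cohort. A last-non-missing rule would fall back to Screening if the Day -1 LCI were missing, which brings back the less suitable value.

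**Conclusion.** No change is needed. The Day 1 line is correct for the spirometry parameters it follows. For LCI and lung volumes it leaves a small gap in the visible text, which the Day -1 Baseline visit fills. For pulse oximetry the missing word is pre-dose, and the intended value is not in doubt.

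The effect is limited to descriptive outputs in at most 16 planned patients of a non-confirmatory study, and to fewer for the LCI endpoint. The primary variable for Cohorts 1 and 2 is adverse events, and the Cohort 3 FEV1 model has its own baseline definition, so neither is touched. No bias is shown, and no result is expected to change.

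This rests on two assumptions: that analysts use the visit labelled Baseline for assessments not scheduled on Day 1, and that the v04 schedule is the one followed. If redacted SAP text already defines an LCI baseline, or v02 had MBNW on Day 1, the SAP as written had no gap for LCI. If the SAP is amended for another reason, the wording could be clarified then, but the point does not justify an amendment.

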### 6.1.3 Statistical model, assumptions and hypotheses

Percent of predicted FEV1 values measured on Day 7, Day 14, Day 21 and Day 28 of each treatment period at the study site for cohort 3 will be analyzed using a mixed effects model for repeated measurements. The model will include fixed effects for period, time (Days 7, 14, 21, 28 as appropriate), treatment and treatment by time. Subject will be included as a random effect and time will be repeated within each patient by period interaction term. Subject-average baseline and period-adjusted baseline will be fitted as covariates. An unstructured covariance matrix will be applied. In case of the analysis fails to converge, compound symmetric covariance structure will be used in the first instance and if further alterations to the model are necessary the significance of the covariates will be explored. Kenward Roger options will be used to calculate the degrees of freedom in all Proc Mixed analysis.

The subject average baseline will be derived as the average of their pre-dose assessments from each period. Period adjusted baseline will be calculated for each subject and for each period, as the difference between the period baseline and the subject average baseline, i.e. value of period baseline - value of average baseline.

The final model estimates will include the LSmean for each treatment together with standard error (SE), the adjusted mean difference between treatments, and 80% two-sided confidence intervals and P-value for the differences. These will be calculated at all time points, and specifically at the primary time point of interest (Day 28) using Placebo as the reference treatment.

No adjustments for multiplicity will be applied for this exploratory study. Missing data is assumed to be Missing At Random (MAR).

Additional summaries of frequencies of responder rates will be presented. A subject will be considered a responder where improvements are seen such that  $FEV1 > 5\%$  or  $LCI > 1$  unit.

#### 6.1.3.1 Model checking procedures

The repeated measures analysis includes all available information in terms of measurements at all times. If missing measurements are missing at random, an analysis of the available data provides consistent estimates of model parameters. Reasons for dropouts will be explored.

Where data has values below and above limits of quantification then the following rule will apply.

In the summary tables, the frequency (n, %) of values below the LLOQ and above the ULOQ, respectively, will be included.

Any values below the limit of quantification will be analyzed as 0.5\*the lower limit, both in the descriptive and the model analysis. Any values above the limit of quantification will be analyzed as 1.0\*the upper limit, both in the descriptive and the model analysis.

No other imputation of missing data is allowed.

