5.2 Prohibited treatment and rescreening

If a patient experiences a respiratory infection or exacerbation which requires systemic antibiotics and/or systemic glucocorticoids at any time, he/she will be discontinued from the study. He/she may be rescreened if he/she subsequently fulfills the required inclusion/exclusion criteria for the study. Note that chronic inhaled and/or systemic antibiotics are permitted as concomitant medications during the study, if they are considered the patient's standard of care at screening and baseline visits.

If a patient is deemed a screened failure, he/she maybe rescreened once based on the investigator's judgement.

Patients who have failed to meet ATS requirements for acceptability/reproducibility for Spirometry or MBNW (Cohorts 1 & 2), will be allowed one additional repeat testing session at Screening and/or Baseline in order to meet inclusion criteria. For additional details on rescreening and retesting, please refer to the site operations manual (SOM).

Patients should refrain from using their short and long acting bronchodilators for 6, 12 or 24 hours as described in the site operations manual (SOM) to enable measurement of trough

lung function. If the patient is not able to withhold rescue medications due to bothersome symptoms, the patient may be rescheduled if deemed appropriate by the investigative site.

Butylcholinesterase and acetylcholinesterase inhibitors are prohibited because QBW276 is hydrolyzed mainly by butylcholinesterase and acetylcholinesterase enzymes. Patients who are either on these inhibitors or patients who fail the butylcholinesterase screening assay will be excluded from the study. The following butylcholinesterase and acetylcholinesterase inhibitors are prohibited:

- Aclidinium bromide
- Amitriptyline
- Citalopram
- Donepezil
- Ecothiopate
- Galantamine
- Lovastatin
- Neostigmine
- Rivastigmine
- Simvastatin
- Sertraline
- Tacrine

Patients who are prescribed these medications during the course of the study should be immediately discontinued from the study and the Sponsor must be informed. The list of prohibited medications is not inclusive and subjects may be exposed to non-medicinal butyrylcholinesterase inhibitors, such as insecticides, which should be monitored.

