7.1 Discontinuation of study treatment

Patients may voluntarily discontinue study treatment for any reason at any time.

Study treatment **must** be discontinued under the following circumstances:

- Patient withdraws consent.
- Pregnancy.
- A serious adverse event that is suspected of being related to study drug.
- The site investigator judges that continuation would be detrimental to the patient's well-being.

- Emergence of the following adverse events:
 - On-treatment increase in QTcF > 60 ms from baseline
 - Clinically significant and/or persistent serum electrolyte or other laboratory abnormalities.
- If a patient has an exacerbation during the study, the patient should be discontinued and may be replaced.
- Use of prohibited treatment as per [Section 5.2](#) and the Prohibited and Concomitant Medication Guidance provided in the SOM.
- Any other protocol deviation that results in a significant risk to the patient's safety.
- Investigator's discretion if the physician perceives a significant risk to the patient's safety or study data integrity.
- Cohorts 1 and 2: if a patient misses ≥ 4 doses, either between visits or consecutive doses overall.
- Cohort 3: if a patient misses ≥ 8 doses, either between visits or consecutive doses overall.

The appropriate personnel from the site and Novartis will assess whether treatment should be discontinued for any patient whose treatment code has been broken inadvertently for any reason.

The appropriate personnel from the site and Novartis will assess whether treatment should be discontinued for a patient who has been prescribed a new standard of care treatment or concomitant medication which may impact the integrity of study data.

Patients who discontinue study treatment or who decide they do not wish to participate in the study further should NOT be considered withdrawn from the study UNLESS they withdraw their consent (see [Section 7.4](#)). Where possible, patients should return for the End of Study assessments listed in the assessment table. If they fail to return for these assessments for unknown reasons, every effort (e.g. telephone, e-mail, letter) should be made to contact them as specified in [Section 7.3](#).

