11.4.3 Handling of missing values/censoring/discontinuations

Cohorts 1 and 2: Patients withdrawn for reasons other than safety and tolerability prior to completion of the Day 7 or 14 assessments may be replaced to gather sufficient data to perform an informed decision on dose selected for the subsequent cohort.

Cohort 3: The repeated measures analysis includes all available information in terms of measurements at all times. If missing measurements are missing at random, an analysis of the available data provides consistent estimates of model parameters. Alternative assumptions may be explored to investigate the robustness of the results under plausible non-Missing at Random situations. Reasons for dropouts will be explored.

Where data has values below and above limits of quantification then the following rule will apply.

In the summary tables, the frequency (n, %) of values below the LLOQ and above the ULOQ, respectively, will be included.

Any values below the limit of quantification will be analyzed as 0.5*the lower limit, both in the descriptive and the model analysis. Any values above the limit of quantification will be analyzed as 1.0*the upper limit, both in the descriptive and the model analysis.

No other imputation of missing data is allowed.

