### 1.2 Study reference documentation

This SAP has been developed using Clinical Trial Protocol version v02 dated 20-Mar-2017.

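### Does the Cohort 3 FEV1 analysis need a pre-specified non-MAR check because patients who exacerbate leave the study?

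*SAP*

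**What the plan says.** **How data are lost.** Protocol 7.1: "If a patient has an exacerbation during the study, the patient should be discontinued and may be replaced". Protocol 5.2 removes from the study a patient with an infection or exacerbation needing systemic antibiotics or glucocorticoids, and adds "He/she may be rescreened if he/she subsequently fulfills the required inclusion/exclusion criteria for the study". After discontinuation, Protocol 7.1 asks only for the End of Study assessments, where possible. Table 8-1 schedules one spirometry at that visit.

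**How data are analysed.** SAP 6.1.3 fits a mixed model to FEV1 at Days 7, 14, 21 and 28 of each period, with Day 28 as the primary time point and 80% two-sided intervals, and it assumes MAR. For the baseline covariates, "The subject average baseline will be derived as the average of their pre-dose assessments from each period". SAP 6.1.3.1 says the analysis uses all available measurements and that reasons for dropout will be examined. It then gives the substitution rule for values outside quantification limits and ends "No other imputation of missing data is allowed".

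**What the protocol adds.** Protocol 11.4.3 contains the same closing sentence, but before it says "Alternative assumptions may be explored to investigate the robustness of the results under plausible non-Missing at Random situations". The readable SAP does not repeat that option. SAP 1.2 states "This SAP has been developed using Clinical Trial Protocol version v02 dated 20-Mar-2017", while the supplied protocol is v04.

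**The concern.** Exit after an exacerbation is linked to the outcome being measured. If exacerbations are more frequent, or deeper, on one treatment, a MAR analysis treats the lost Day 28 values as if those patients had followed the course predicted from their earlier visits. The Day 28 difference could then look better or worse than the difference across everyone randomised. The readable SAP offers only a look at dropout reasons, which can show an imbalance but not its effect on the estimate. Read literally, the imputation sentence would also rule out delta-adjusted multiple imputation, a usual tool for this question.

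Two details looked open as well. A patient who leaves in Period 1 has no Period 2 pre-dose value for the subject-average baseline, so a careless program might drop that patient. And no readable analysis rule covers a patient who is rescreened.

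**Working it through.** **1. The plan's own figure.** Protocol 11.6 allows up to 40 randomised to obtain 24 completers: 1 − 24/40 = 40% non-completion. Attrition was anticipated. No dropout rate, effect size or SD for Cohort 3 is readable, so every exit rate, fall and SD below is an assumption.

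**2. The imputation sentence in context.** In both documents it comes straight after the quantification-limit rule, and *other* refers back most naturally to that rule. In Protocol 11.4.3 it shares a section with the permission to explore non-MAR assumptions, so a total ban would sit badly with its own section. Even read literally, it leaves likelihood-based and closed-form pattern-mixture methods open.

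**3. The gap between two targets.** With the same fall under both treatments and the fall not recorded before exit:

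MAR estimate − all-patient difference = fall × (exit rate on drug − exit rate on placebo)

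- 3 points, 15% vs 10%: 3 × 0.05 = 0.15
- 8 points, 20% vs 10%: 8 × 0.10 = 0.80
- 10 points, 20% vs 10%: 10 × 0.10 = 1.0
- equal rates: 0
- rates reversed: same size, opposite sign

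**4. Simulation.** 2,000 crossovers per case; true effect 3; entry until 24 complete or 40 are randomised; subject SD 3, residual SD 3.5, within-period AR(1) correlation 0.6; exacerbation onset uniform over the four visits; exit removes all later data. Baseline covariates were not simulated.

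| Case | MAR estimate, fall unmeasured | All-patient | Gap, unmeasured | Gap, fall measured at exit visit |
|---|---|---|---|---|
| 3 points, 15% vs 10% | 3.01 | 2.86 | 0.15 | 0.06 |
| 8 points, 20% vs 10% | 2.97 | 2.20 | 0.77 | 0.29 |
| 10 points, 20% vs 10% | 3.03 | 2.02 | 1.01 | 0.34 |

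The Monte Carlo SE of a gap is 0.01 to 0.02. Reversing the rates in the 8-point case gives −0.79 and −0.29. Equal rates (15% each, 8 points) give −0.03 to 0.03. Estimating the planned covariance by REML (250 runs, 8-point case) gives 0.77 and 0.22. In the unmeasured column the MAR model recovers the effect without exits; the gap is the distance to a different target.

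**5. Against precision.** The SD of the estimate was 0.95, so the 80% half-width is 1.28 × 0.95 = 1.22. Every gap in the table is smaller. Larger assumed imbalances are not: 30% vs 10% missing with a 10-point fall gives 10 × 0.20 = 2.0, and the ceiling of 40% on one treatment and none on the other gives 4.0.

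**6. When the 80% interval would stop excluding zero.** With 20% vs 10% exits, the same delta under both treatments and variance 0.95² + 0.0080 × delta², solve estimate + 0.10 × delta = 1.28 × √variance:

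- estimate 1.5, delta −2.5: 1.25 against 1.28 × √0.9525 = 1.25
- estimate 2.0, delta −6: 1.40 against 1.28 × √1.1905 = 1.40
- estimate 2.5, delta −9: 1.60 against 1.28 × √1.5505 = 1.59
- estimate 3.0, delta −10: 2.00 against 1.28 × √1.7025 = 1.67, zero still excluded

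**7. Period 1 exits.** With one available baseline b, the subject average is b and the period-adjusted baseline is b − b = 0. The patient stays in the model, as the all-available-data statement in SAP 6.1.3.1 implies. Dropping these patients instead (4 to 5 of them) would raise the measured gaps from 0.06, 0.29 and 0.34 to 0.09, 0.50 and 0.59.

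**The case for a change.** The best case for a change is that attrition is planned for, exit depends on lung health, and the 80% interval is the reported result. A half-width describes random error and does not excuse a systematic shift, and step 6 shows that estimates of 1.5 to 2.5 can lose exclusion of zero within deltas of 0 to −10. The permission in Protocol 11.4.3 is optional and names no method. Choosing deltas after unblinding is weaker than fixing them beforehand, and one supportive analysis costs little.

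Much of this stands as advice. It does not establish a fault. The shift needs unequal exits or falls between treatments, and nothing readable says they would be unequal or in which direction. With about 33 randomised and exits of 20% vs 10%, roughly 6 against 3 patients carry the whole adjustment.

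The absence itself is uncertain. Protocol 11.4.4 (Supportive analyses) is in the contents but its text is not shown, SAP text after 6.1.3.2 is redacted, and the SAP was written from an earlier protocol version.

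A delta analysis is no neutral referee either. In the 8-point case with the fall measured at exit, the MAR estimate is 2.20 + 0.29 = 2.49. Three quarters of exits then lack Day 28, so the missing shares differ by 0.75 × 0.10 = 0.075. A delta of −8 gives 2.49 − 0.60 = 1.89, an overcorrection against 2.20, while −3 gives about 2.27.

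On rescreening, Protocol 5.2 refers details to the site operations manual. Full re-entry after exposure to the drug would also sit badly with the stated aim of at most four weeks of QBW276 in a lifetime, so such cases should be few.

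**Conclusion.** No change to the plan is needed. The quoted text is accurate and the missing-data mechanism is plausible, but the MAR model is a defensible primary analysis for a non-confirmatory Phase Ib/IIa crossover whose objective is pharmacodynamic response and whose exits may be replaced. The protocol already leaves non-MAR work open, and the imputation sentence does not block it.

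The baseline question is a gap that an analyst would fill sensibly by using the available value. Protocol 5.2 (removal from the study) and 7.1 (not withdrawn unless consent is withdrawn) are worded differently and should be read together. On either reading no scheduled Day 7 to 28 visits are requested after exit, so the model receives the same data.

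The size is 0 to about 1 point of percent predicted FEV1, in either direction, for falls up to 10 points and exit-rate differences up to 10 percentage points, against a half-width near 1.2. It rests wholly on assumed rates, falls and SDs, and step 5 shows that a more lopsided split would exceed that range. The dropout reasons that the SAP undertakes to examine would reveal such a split. If one appeared, the exploration allowed by Protocol 11.4.3 would be the natural response.
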